Official Title: Personalized Mobile Phone App Intervention: Challenging Alcohol Expectancies to Reduce High-risk Alcohol Use and Consequences

NCT number: NCT04213846

Document Date: May 24, 2024

STUDY PROTOCOL

The purpose of the study is to develop and test a smartphone/mobile app intervention to target high-risk alcohol use among young adult college students. The intervention incorporates three weeks of ecological momentary assessment (EMA, i.e., two brief surveys per day) and daily intervention messaging (2 messages per day). The intervention content mainly focuses on alcohol expectancies, alcohol use, and consequences and how these constructs are interrelated and includes personalized intervention messages based on participants' own event-level alcohol expectancies and experiences. Other psycho-educational alcohol-related content is also provided over the course of the three-week intervention.

The study design is a randomized clinical trial; participants are randomized to either the intervention condition or to an assessment-only condition. All participants completed an online or in-person informational/training session, an online baseline assessment, twice-daily surveys for 21 days, and online 1-month, 6-month, and 12-month follow-up assessments with additional twice-daily surveys for 14 days at each follow-up period.

College students were recruited from registrar's lists from three college campuses in the Seattle metropolitan area (i.e., two community colleges and one 4-year university) and sent initial information about the study via US mail. Students also received an email with an invitation to participate in an online screening survey to determine eligibility for the larger study. For those who went to the screening survey, they were first presented with an information statement and asked to electronically consent to participation.

To supplement these methods, recruitment also took place through social media, newspaper and other online advertisements and flyers posted around local colleges and nearby businesses. Interested individuals were directed to the study website to review an information statement and participate in a brief survey to obtain contact information and initial screening items. Participants who met initial criteria were contacted by study staff to verify their identity before proceeding to the full study screening process.

Participants who met eligibility criteria on the screening survey were presented with an information statement for the full longitudinal study. Upon providing electronic consent, participants completed a 30-35 minute baseline assessment. At the completion of the baseline survey, students were asked to schedule a training session conducted either in-person or virtually via Zoom. Prior to the training session, participants were randomized to one of two conditions (i.e., intervention condition or assessment-only control condition) by computer algorithm and stratified on biological sex, typical drinks per week, and college status. During the training session, participants were shown a PowerPoint presentation to aid in a discussion of the EMA survey process and study procedures, had the opportunity to ask study staff questions, and installed the web-based application on their mobile phone. Participants randomized to intervention condition had the capabilities within the app for EMA data collection and for viewing intervention content, whereas those randomized to the control condition only had the ability to utilize the app for EMA data collection. After completing the training session, participants were considered enrolled in the study.

The day after the training session, participants in both conditions completed twice daily surveys in the mobile app for 21 days. Morning assessments could be completed between 8am and 1pm. Afternoon assessments could be completed between 3pm and 7pm. Participants in the intervention condition also received intervention messages twice a day (timed to occur after completion of the assessment or generated at 1pm and 7pm, whichever was sooner).

Participants were asked to completed online follow-up assessments at 1-, 6-, and 12-months post-intervention. Follow-up assessments include both an online survey and 14 days of twice-daily EMA assessments. Participants received follow-up calls, emails, and text messages at each follow-up assessment.

Participants were compensated with Amazon.com eGift cards for completion of surveys with a total compensation of up to \$435 if they completed all assessments. Participants received \$20 for the Screening survey, \$25 for the Baseline survey, \$2 for each completed Daily EMA survey (2x/day for 21 days after baseline survey) with \$84 possible, \$20 for the 1-month follow-up survey, \$30 for the 6-month follow-up survey, and \$35 for the 12-month follow-up survey. Follow-up daily EMA assessments were compensated at the rate of \$2 for each completed assessment (2x/day for each 14 days period) with total \$168 possible. A bonus of \$7 per week during the EMA periods was also received if 12/14 surveys are completed each week with \$63 possible across the study period.

## Statistical Analysis Plan

The primary aim of this paper is to examine the efficacy of the intervention on short-term (1-month versus baseline) and long-term (6- and 12-months versus baseline) alcohol outcomes using planned contrasts. Given the repeated measures design and that all outcome variables will be non-normally distributed, generalized linear mixed models (GLMMs) will be used to test intervention effects and logistic, Poisson, negative binomial, and/or gamma error distributions may be used (Hox et al., 2017; Raudenbush & Bryk, 2002). Models will be estimated using the *glmmTMB* (Brooks et al., 2017) package in R 4.2.1 (R Core Team, 2022) using maximum likelihood estimation based on the Laplace Approximation. Four models will test for intervention effects on primary alcohol outcomes. The primary outcomes will be (1) number of typical drinks per week in the past month, (2) number of HED days in the past two weeks, (3) peak eBAC in the past month, and (4) total number of negative alcohol consequences experienced in the past month. Models use data from assessments at four timepoints (screening/baseline, 1-, 6-, and 12-month follow-ups), yielding up to 1,632 Level 1 observations across 408 Level 2 cases. All models will control for sex and college type (enrollment at 2-year versus 4-year college) at Level 2. This model serves as the basis for testing intervention effects on primary alcohol outcomes: Level 1:

$$\begin{aligned} \text{Level 1: } \text{Outcome}_{ti} &= \pi_{0i} + \pi_{1i}(1\text{-month})_{ti} + \pi_{2i}(6\text{-month})_{ti} + \pi_{3i}(12\text{-month})_{ti} \\ \text{Level 2: } \pi_{0i} &= \beta_{00} + \beta_{01}(\text{Intervention})_i + \beta_{02}(\text{Sex})_i + \beta_{03}(\text{College})_i + r_{00i} \\ \pi_{1i} &= \beta_{10} + \beta_{11}(\text{Intervention})_i + r_{10i} \\ \pi_{2i} &= \beta_{20} + \beta_{21}(\text{Intervention})_i + r_{20i} \\ \pi_{3i} &= \beta_{30} + \beta_{31}(\text{Intervention})_i + r_{30i} \end{aligned}$$

where  $t$  indexes study wave and  $i$  indexes individual participants.  $\text{Outcome}_{ti}$  represents the value of the outcome variable for a given individual at a given study wave. To test for intervention effects, time will be coded with a set of binary indicator variables (1-month, 6-month, 12-month) that compare each follow-up wave to screening/baseline (reference category). Intervention is a binary variable comparing the intervention condition to the assessment-only control condition. Of particular interest are parameters that reflect the interaction between intervention group and study wave (e.g.,  $\beta_{11}$  at 1-month). The outcome will be connected to predictor variables through a link function, which will vary based on the type of error distribution used (e.g., log link function for Poisson error distribution). Sensitivity analyses will include linear or non-linear growth models testing average monthly changes in alcohol outcomes between the control and intervention conditions rather than the planned contrasts described above.

A secondary aim will test whether the intervention resulted in long-term (12 month) reductions in level of hazardous/harmful drinking, as indicated by AUDIT scores, as compared to the control condition. This will be tested using a negative binomial regression in which AUDIT scores at the 12-month follow-up will be regressed on condition, sex, college type, and baseline AUDIT scores.

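### Must the SAP say how zero peak eBAC values are handled, and which part of a two-part model is the primary test?

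*SAP*

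**What the plan says.** All of the relevant text is in the SAP section headed Statistical Analysis Plan.

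- The third primary outcome is "3) peak eBAC in the past month". The other three are numbers of drinks, heavy-drinking days and consequences.
- Mixed models are chosen because "all outcome variables will be non-normally distributed", and "logistic, Poisson, negative binomial, and/or gamma error distributions may be used". No family is assigned to any primary outcome.
- "Four models will test for intervention effects on primary alcohol outcomes". One two-level equation is displayed, introduced by "This model serves as the basis for testing intervention effects on primary alcohol outcomes".
- The data are described as "yielding up to 1,632 Level 1 observations across 408 Level 2 cases".
- "Of particular interest are parameters that reflect the interaction between intervention group and study wave", and "The outcome will be connected to predictor variables through a link function, which will vary based on the type of error distribution used".

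The section does not mention zeros, a hurdle or other two-part model, or a rule for combining two parts. For the secondary AUDIT analysis, by contrast, it names a single family, the negative binomial.

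**The concern.** Peak eBAC is continuous, and it is zero for a participant who drank nothing in the month. Gamma is the only listed family that suits a continuous outcome by itself, and its support excludes zero. Once a zero occurs, the analyst must drop rows, add a constant, or split the outcome into a zero part and a positive part. The section does not say which, nor which part would carry the primary test.

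Two things could be at stake.

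- **The question answered.** A test of the positive part alone compares participants still drinking at that wave. That group is formed after randomisation, so students whom the app led to stop drinking would drop out of the comparison.
- **Error control.** If the choice is made after the zeros are seen, or a win on either part is counted, the false-positive risk for a contrast rises.

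**Working it through.** **1. The plan's own figure.** 408 participants × 4 timepoints = 1,632, as stated. This maximum counts every participant at every wave and makes no deduction for non-drinkers.

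**2. Matching families to outcomes.** Poisson and negative binomial suit the three counts, and gamma suits positive eBAC. Logistic suits none of the four outcomes taken whole. Its natural use here is a zero/non-zero part. The list therefore plausibly allows a logistic-plus-gamma model, and the displayed equation is described only as a basis.

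**3. Can zeros slip through unnoticed?** The gamma log-density at zero is −∞ for shapes 2 and 4, +∞ for shape 0.5, and finite only at shape 1. In glmmTMB 1.1.9 under R 4.3.3 (the plan names R 4.2.1), a gamma model with log link stopped with an error on non-positive values. The hurdle form in the same package returned a fit.

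**4. Size of the difference.** The documents give no abstinence rates, so every rate here is assumed. For raw means at one wave,

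overall ratio = positive-only ratio × (1 − p_int)/(1 − p_ctl),

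where p is the share with zero eBAC in each arm. Suppose drinkers' eBAC is unchanged (positive-only ratio 1.00). The standard error (SE) of one wave's log ratio with 408 participants is about 0.10; the simulated values used below are 0.093 at 2% v 3% and 0.099 at 10% v 15%.

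| Control v intervention abstinence | Overall ratio | Log gap | Gap in SEs |
|---|---|---|---|
| 2% v 3% | 0.97/0.98 = 0.990 | 0.010 | 0.010/0.093 = 0.1 |
| 5% v 7.5% | 0.925/0.95 = 0.974 | 0.027 | 0.027/0.10 = 0.3 |
| 10% v 15% | 0.85/0.90 = 0.944 | 0.057 | 0.057/0.099 = 0.6 |

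If the two arms have equal zero shares, the factor is 1 and the gap vanishes.

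A large-sample random-intercept gamma model fitted to the positive rows (shape 2.5, random-intercept SD 0.6) gave these interaction ratios, with the overall mean ratio in brackets:

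| Who the extra abstainers are | 2% v 3% | 10% v 15% |
|---|---|---|
| Random | 1.000 (0.990) | 0.999 (0.945) |
| From the lightest third | 1.006 (0.997) | 1.039 (0.984) |
| From the heaviest third | 0.993 (0.980) | 0.956 (0.882) |

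The largest gap is the heaviest-third case at 10% v 15%: ln(0.956/0.882) = 0.081, and 0.081/0.099 = 0.8 SE. At 2% v 3% the same case gives ln(0.993/0.980) = 0.013, and 0.013/0.093 = 0.1 SE.

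**5. Error rate if either part may win.** At an assumed two-sided 0.05 with independent parts, 1 − 0.95² = 0.0975; simulation gave 0.093 to 0.099. With one named part, a joint two-degree-of-freedom test, or the overall mean, simulation gave 0.048 to 0.053.

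**6. Is one primary test clearly best?** A simplified one-wave simulation (204 per arm, gamma shape 2, no random effects, so not the SAP's model) gave the following power at 5%/10%/20% control zeros.

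| Test | Zero share +8 points only | Positive mean −15% only |
|---|---|---|
| Zero part | 0.82/0.64/0.47 | about 0.05 |
| Gamma part | about 0.05 | 0.62/0.61/0.55 |
| Joint test | 0.74/0.54/0.38 | 0.51/0.51/0.44 |
| Overall mean | about 0.19 | 0.58/0.53/0.42 |

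No row is best in both columns.

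**The case for a change.** The strongest case for a change is that a primary outcome is specified less fully than the secondary AUDIT analysis, that zeros are foreseeable, and that naming one test in advance costs little. If a two-part model was never intended, the difficulty is sharper, because a plain gamma model cannot keep those rows. The single equation and the count of four models do read more naturally as one linear predictor per outcome. The stated observation count is also a ceiling, so it does not prove that zeros stay in.

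Much of this stands. The section assigns no family to eBAC and is silent on zeros, and counting a win on either part would nearly double the risk for that contrast. But nothing in the plan licenses such counting, restricts the test to positive values, or tells anyone to drop zeros. Those are fears about how a permissive sentence might be used.

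Nor is there an obvious replacement. A hurdle-gamma model tested on the overall mean keeps all observed participants in the comparison, but it loses most of its power when the effect is on zeros alone. It can also fail at the reference wave. With no zeros at baseline, which is possible if eligibility required recent drinking, the logistic part is separated: a trial fit with 204 per arm and 10% v 15% zeros at follow-up gave an intercept of −26.6 and standard errors of about 25,000 to 35,000. The simulations of that contrast used observed zero shares, not averaged model predictions, and left out the plan's random wave terms.

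**Conclusion.** No change follows. This is missing detail in a deliberately permissive plan, and an analyst can fill it sensibly with families and software the plan already names. The software error on zeros means the matter cannot pass unnoticed.

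Under the assumed rates, testing the positive part alone would differ from the overall contrast by 0.1 to 0.6 SE if the extra abstainers stop at random, and by up to about 0.8 SE if they come from the heaviest third at 10% v 15%. In all of these cases abstinence is higher in the intervention arm, so the positive-only ratio understates the benefit; the reverse imbalance would reverse that. The documents give no zero rates by arm or wave, so neither size nor direction can be established, and the effect may be negligible.

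The conclusion rests on reading the logistic entry as allowing a zero part, which the text permits but does not state. It also assumes 1:1 allocation for the per-arm figures, and it covers only the section headed Statistical Analysis Plan.

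### Does the four-random-effect negative binomial model need a prespecified fallback because it often fails to converge cleanly?

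*SAP*

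**What the plan says.** The Level 1 / Level 2 equations in the SAP (Statistical Analysis Plan) put a person-level residual on the intercept and on each of the three wave coefficients. Of time, the SAP says that "time will be coded with a set of binary indicator variables (1-month, 6-month, 12-month) that compare each follow-up wave to screening/baseline". The data are described as "yielding up to 1,632 Level 1 observations across 408 Level 2 cases". On error families, it says "logistic, Poisson, negative binomial, and/or gamma error distributions may be used". Fitting is in glmmTMB "using maximum likelihood estimation based on the Laplace Approximation".

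The contrasts that matter are the wave-by-arm terms β11, β21 and β31: "Of particular interest are parameters that reflect the interaction between intervention group and study wave". The one other model named for the primary outcomes is a growth model: "Sensitivity analyses will include linear or non-linear growth models testing average monthly changes in alcohol outcomes". It takes the place of the planned contrasts, so it cannot stand in for them if the main fit fails.

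The text available does not give a covariance structure for the four residuals, an optimizer, or a rule for a failed fit. Part of the SAP was not available to read, so this silence can be asserted only of the text supplied.

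**The concern.** Three of the four primary outcomes are counts, so a negative binomial family is a natural choice. With one random effect per observation, the random effects can already absorb the overdispersion, and the dispersion parameter then competes with them. A statistician would expect weak identification and warnings from the software.

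If the fit fails, someone must accept it or replace it with the outcome data in view. At stake are the tests of β11, β21 and β31 on the count outcomes. A replacement chosen because of its result, or one with standard errors that are too small, would weaken the primary analysis.

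**Working it through.** **The plan's own figure.** 408 people × 4 waves = 1,632 observations, as stated, so at most 4 per person.

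**Parameter count, if the effects are freely correlated (the default reading, not SAP text).** 4 variances + 6 covariances = 10; adding 1 dispersion parameter gives 11. Four waves supply 4 + 6 = 10 second moments.

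**Where the redundancy lies.** Assume a log link, normal effects with covariance s, marginal mean m and negative binomial size θ:

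- Cov(Y_t, Y_u) = m_t m_u (exp(s_tu) − 1)
- Var(Y_t) = m_t + m_t² (exp(s_tt)(1 + 1/θ) − 1)

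Only s_tt + log(1 + 1/θ) enters the variance. Take θ = 3, shared variance 0.5 and wave-specific variance 0.10. Then 0.10 + log(4/3) = 0.10 + 0.288 = 0.388, and θ = 1/(exp(0.388) − 1) = 2.11 with no wave-specific variance gives the same moments. At m = 2.5 both give Var = 2.5 + 6.25 × 1.4295 = 11.43. Dispersion and wave variance can be told apart only through higher-order features of the data.

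**What this does to the contrasts.** Under the same assumptions, with the covariance equal in both arms, log E(Y_t) is the linear predictor plus s_tt/2. The s_tt/2 term cancels in the arm comparison at each wave. The arm difference at 1 month less that at baseline is (β01 + β11) − β01 = β11, whatever the split between dispersion and wave variance. The ridge is in the variance parameters.

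**How often the fit fails.** These are simulations in glmmTMB 1.1.9 (R 4.3.3, where the SAP names R 4.2.1) with default settings. All means, dispersions and variances are assumed. Failure means a Hessian that is not positive definite.

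| Data | Four correlated effects, negative binomial | Random-intercept negative binomial | Four correlated effects, Poisson |
|---|---|---|---|
| Complete, θ = 3, three scenarios | 53 + 37 + 44 = 134 of 174 failed | 0 of 174 failed | not run |
| 12% missing at each follow-up, eight scenarios | 54 of 77 failed (3 of 9 to 10 of 10 by scenario) | 0 of 77 failed | 0 of 77 failed |
| Complete, decaying correlation, means 2.5 and 8 | 43 of 47 and 33 of 48 failed | 0 of 95 failed | 0 of 95 failed |

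A retry with the BFGS optimizer cut failures from 22 of 29 to 12 of 29 (41%), although 17 of 29 still missed a stricter standard that also excludes boundary or runaway estimates. Gamma failed in 4 + 5 = 9 of 116 fits (7.8%).

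**What it costs the inference.**

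- The p<0.05 verdict differed between the four-effect and random-intercept fits in 5 of 522 negative binomial and 5 of 348 gamma contrasts: 10/870 = 1.1%.
- With 12% missing, the 1-month standard error relative to the random-intercept negative binomial fit had median 1.00 for the four-effect negative binomial and 1.01 for the four-effect Poisson. The range over both was 0.91 to 1.07.
- At 12 months with decaying correlation, failed negative binomial fits and four-effect Poisson fits gave standard errors of 0.143 against 0.144 in one scenario and 0.123 against 0.124 in the other.

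**The case for a change.** The best case for a change is that the SAP leaves the replacement open and one obvious replacement is not harmless. A random intercept with model-based errors imposes equal correlation between waves. If correlation decays, its 12-month standard error was 0.92 to 0.95 of the empirical value for negative binomial data, so 5% to 8% too small, and 0.85 for gamma. False positives at 12 months were 66 of 800 (8.3%) for negative binomial with mean 8 and 82 of 800 (10.3%) for gamma. Person-clustered errors brought these to 47 (5.9%) and 57 (7.1%). The remedy would be to prescribe a random intercept with clustered or bootstrap errors for every negative binomial and gamma outcome.

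The warning about that fallback stands, but the understatement belongs to a model the SAP does not specify. The prescription is itself a debatable trade:

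- It discards three of the four Level 2 residuals and the unstructured wave covariance.
- It covers gamma, where only 7.8% of fits failed and where the clustered test still rejected 7.1% (95% CI 5.4% to 9.1%).
- Clustered errors were not tested with missing follow-ups, and the bootstrap was not tested at all.
- It passes over Poisson with the four effects, which keeps every equation and planned contrast and drops the parameter that causes the trouble.

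The claim that the model as written usually fails also rests on free correlation, which the SAP does not state. Uncorrelated negative binomial effects gave no warning in 24 of 24 fits, though 15 of those had a standard deviation at zero.

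**Conclusion.** No change is called for. If the four residuals are freely correlated and a negative binomial family is used, default glmmTMB fits often fail the Hessian check: 33% to 100% by scenario in the data with missing follow-ups, and fewer after a change of optimizer. The text available does not say what happens then. What was not shown is harm to β11, β21 or β31. Standard errors agreed closely across structures and about 1% of verdicts changed. The four-effect Poisson model, within the SAP's stated families, was clean in 77 + 95 = 172 of 172 fits. An analyst who met the warning could drop the redundant dispersion parameter and keep the planned contrasts.

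This rests on assumed parameter values and a newer R version than the SAP's. The false-positive rate of the four-effect model itself was not measured, so the conclusion is that no damage was demonstrated, not that none is possible.

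### The drinks-per-week model uses neither the stratification on drinks per week nor the baseline equality that randomisation provides, so its intervention-by-wave contrasts are less precise than they need be

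*SAP*

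**What the plan says.** - Randomisation (Protocol, paragraph on consent, baseline and training): participants were allocated "by computer algorithm and stratified on biological sex, typical drinks per week, and college status". The cut-points for drinks, the allocation ratio and any blocking within strata are not given.
- Outcome (SAP, Statistical Analysis Plan): "The primary outcomes will be (1) number of typical drinks per week in the past month".
- Covariates (SAP, same section): "All models will control for sex and college type (enrollment at 2-year versus 4-year college) at Level 2". In the equations, sex and college appear only in the intercept, pi0i. The wave equations pi1i, pi2i and pi3i contain intervention and a random effect, nothing else.
- Tested terms (SAP, same section): "Of particular interest are parameters that reflect the interaction between intervention group and study wave". Screening/baseline is the reference wave. Baseline is thus a row of the response, and beta01 lets the arms differ there.
- Error distribution (SAP, same section): "logistic, Poisson, negative binomial, and/or gamma error distributions may be used".
- Secondary aim (SAP, same section): "AUDIT scores at the 12-month follow-up will be regressed on condition, sex, college type, and baseline AUDIT scores". That model already contains the baseline value of its own outcome.

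**The concern.** One of three stratification factors is missing from every model, without a reason given, and it shares its name with the first-listed primary outcome.

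People who drink heavily at baseline tend to show larger falls, through regression to the mean, so baseline drinking predicts the change that beta11, beta21 and beta31 compare between arms. Nothing in pi1i-pi3i removes that variation. Nor does the model use the fact that both the screening and baseline surveys precede randomisation, so that the arms have the same expected baseline.

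What is at stake is confidence-interval width and power for drinks per week. How the loss shows itself depends on allocation within strata:

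- Under restricted allocation (for example permuted blocks), the model standard error ignores balance that was achieved, so the test is conservative.
- Under unrestricted allocation, the test is close to its nominal level, but the estimate varies more than it needs to.

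**Working it through.** **Inputs from the documents.** 408 participants and four waves: 408 × 4 = 1,632, which reproduces the SAP's maximum number of Level 1 observations.

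**Assumptions, not in the documents.** Equal arms (204 each), two-sided 5% level, equal SD at each wave, complete data, linear scale, a two-level stratum split at the median of the wave-0 value, and baseline-to-follow-up correlation rho = 0.8, 0.6 or 0.3.

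**1. Variance of change explained by the stratum.** With unit SD, change has variance 2(1 − rho). Baseline explains (1 − rho)² of it, and a median split keeps 2/pi of that. So R² = (1 − rho)²(2/pi) / [2(1 − rho)] = (1 − rho)/pi, and k = 1/√(1 − R²). Power is set at 80% for the stratum-adjusted model (a shift of 2.80 standard errors).

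| | rho 0.8 | rho 0.6 | rho 0.3 |
|---|---|---|---|
| R² | 0.064 | 0.127 | 0.223 |
| k | 1.033 | 1.071 | 1.134 |
| Blocked: SE too wide by k − 1 | 3.3% | 7.1% | 13.4% |
| Blocked: type I error, 2Φ(−1.96k) | 4.3% | 3.6% | 2.6% |
| Blocked: power, Φ(2.80 − 1.96k) | 78.1% | 75.9% | 71.9% |
| Unrestricted: cut in SD, 1 − 1/k | 3.2% | 6.6% | 11.8% |
| Unrestricted: power, Φ(2.80/k − 1.96) | 77.4% | 74.5% | 69.5% |

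A linear simulation (n = 408, 8 strata, blocks of 4, 10,000 runs) gave planned SE/SD of 1.035/1.069/1.119 and type I error of 4.4%/3.6%/3.0%, slightly milder than the formula at rho 0.3.

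**2. Source of the stratum.** If it came from a separate measure correlated 0.8 with wave 0 and 0.6 with follow-up, then at rho 0.6 R² = (0.8 − 0.6)²/(2 × 0.4) × 2/pi = 0.032 and k = 1.016. The excess falls from 7.1% to 1.6%.

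**3. Stratum in the intercept only.** A time-constant covariate in pi0i cancels out of each person's change. In complete-data Gaussian fits at rho 0.6, the three estimates and SEs were identical with and without it, to about 1e-14 (1-month SE 0.0871 both ways). With 15% missing at each follow-up, the SE was 0.0938 with it and 0.0935 without. A 200-run Poisson GLMM gave SEs of 0.0838 and 0.0817. There is no gain.

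**4. Fixes that do help, linear scale.** With a common baseline mean, the residual variance is 1 − rho² instead of 2(1 − rho), a ratio of (1 + rho)/2: 0.90, 0.80 and 0.65. Now set the planned contrast at 80% power. The common baseline gives Φ(2.80/√0.80 − 1.96) = 87.9% at rho 0.6, and 84.0% at 0.8. Stratum-by-wave terms give Φ(2.80k − 1.96) = 85.1% and 82.5%.

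**5. Poisson GLMM simulation.** Two waves, Laplace maximum likelihood, 4,000 runs, assumed mean about 10 and log-SD 0.7, rho on the log scale. Power is at a shift of 2.80 SDs of the stratum-adjusted estimate. The Monte Carlo SE of type I error is about 0.35 points. Cells give rho 0.8/0.6/0.3.

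| | Type I error, % | Power, % |
|---|---|---|
| Blocked, as planned | 4.2/3.5/2.0 | 78.4/75.3/69.9 |
| Blocked, stratum in intercept and wave term | 5.4/5.3/4.5 | 80.8/79.7/77.8 |
| Blocked, no beta01 | 5.2/5.8/4.2 | 84.8/85.1/86.9 |
| Unrestricted, as planned | 5.2/5.0/5.5 | 77.8/73.3/71.5 |
| Unrestricted, stratum in intercept and wave term | 5.2/4.7/5.6 | 81.3/79.7/81.9 |
| Unrestricted, no beta01 | 5.3/5.3/5.3 | 85.2/85.9/89.3 |

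**6. Cost of omitting the drinks stratum for the other outcomes.** For HED days, peak eBAC and consequences, R² = r²(1 − rho)/pi, where r is the assumed correlation with baseline drinking. For r = 0.5 and rho = 0.6, k = 1.016, an excess of 1.6%. The range is 0.3% (r = 0.3, rho = 0.8) to 6.0% (r = 0.7, rho = 0.3). For AUDIT, given its own baseline, it is 0 to 0.6%.

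**The case against.** The strongest reply is that baseline drinking is already in the model, as the reference wave with person-level random effects, so the stratum would only be a coarse copy of a response row. The first half is true but does not restore the precision. Because beta01 is free, the contrast reduces to a raw change score on the linear scale with complete data. The second half stands, and is a reason to prefer the common-baseline model to stratum terms.

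A reader might infer from the covariate sentence that naming the third factor there would cure the problem. The SAP's own equations do not support that: covariates named there enter pi0i only, where the stratum does nothing for the tested contrasts. The loss comes from the free baseline difference and the absence of wave terms. That it persists under unrestricted allocation shows that it is partly the general inefficiency of a change contrast.

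Three further objections stand. The size rests on assumed correlations, a median split and the stratum's source; at rho 0.8 it is only 2 to 3 power points by the formula. The GLMM check covers two waves and a Poisson error only; negative binomial, gamma and logistic models were not simulated, and with a logistic link the SE may not fall. The change would also come late: the Protocol, dated May 24, 2024, describes study conduct largely in the past tense, and the SAP already counts 408 cases.

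**Conclusion.** The point holds as one of efficiency, of low to moderate importance. For drinks per week, the planned contrasts forgo precision that the design makes available.

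Under the stated assumptions, ignoring the stratum makes the SE about 3%, 7% or 13% too wide (rho 0.8, 0.6, 0.3) if allocation was blocked. If allocation was unrestricted, adjustment would cut the sampling SD by about 3%, 7% or 12%. At rho 0.6 the SE excess is only about 1.6% if the stratum came from a separate measure. The Protocol does not settle the source or the blocking. For the other outcomes the cost of ignoring this stratum is small under central assumptions.

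A reader might infer that omitting a stratification factor biases the effect or invalidates the test. The documents and the calculations do not support this: the planned test is nominal or conservative, and no outcome gains false positives.

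**What to change.** 1. In the drinks-per-week GLMM, drop beta01, so that both arms share one baseline mean. This recovers the most power in the checks above, needs one parameter fewer and does not condition on a function of a response row. It relies on baseline being measured before randomisation, which the Protocol describes. Since the Protocol counts people as enrolled only after the later training session, the sponsor should state whether the 408 are those randomised or those enrolled and, if the latter, that losses in between were unrelated to arm.
2. Alternatively, add the randomisation stratum, in the categories used, to pi0i and also to pi1i-pi3i. With two levels this adds 4 fixed effects (1 main effect and 3 wave terms) against up to 1,632 observations.
3. State whether the stratum uses the wave-0 value of the outcome and whether allocation within strata was blocked.
4. Keep the model as written as a sensitivity analysis.

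The other three GLMMs carry the same free beta01, and the variance ratio in step 4 is not specific to drinks. Applying one rule to all four would be a general efficiency choice, separate from the stratification point. Sex-by-wave and college-by-wave terms are optional.

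The cost is SAP wording and a dated justification for a late change to one primary model; no new data are needed. Simulated type I error after either fix was 4.2% to 5.8%. The chosen error distribution should be checked in the same way, with four waves, before the change is adopted.
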